3.2 Study Flow and Follow up Schedule

Consecutive eligible patients that present for MitraClip procedure should be consented for the MitraClip EXPAND G4 Study. Patients are included in the analysis upon completion of MitraClip G4 procedure.

Follow-up data on clinical assessment should be submitted at discharge, 30-day visit, 6-month phone call, 1 year, 2 year, 3 year, 4 year and 5 year visits. Echocardiograms are required to be submitted for the baseline, discharge, 30-day and 12-month and 5 year time points. All Echocardiograms conducted by the site during the study period (required by protocol or not) will be submitted to the Sponsor (see **Table 2**). Section 6.4 of this protocol provides more detail on follow-up visits.

The first █ subjects treated with the MitraClip G4 in the MitraClip EXPAND G4 Study in Europe with evaluable acute procedural success (APS) data will be included in the G4 PMCF Study as described in Appendix II. Subjects with evaluable echocardiograms may be selected for a more detailed assessment by an independent core lab.

A schematic of the study flow is shown in **Figure 2**.

3.3 Early Termination of the Clinical Study

No formal statistical rule for early termination of the MitraClip EXPAND G4 Study is defined.

The Sponsor reserves the right to discontinue the study at any stage or reduce the follow up period with suitable written notice to the investigator. Possible reason(s) may include, but are not limited to:

- Further product development is cancelled.

Should the study be discontinued by the Sponsor, patients will be followed up as per routine hospital practice with device related AEs being reported to the Sponsor as per vigilance/commercial reporting requirements. Should this occur, the investigator shall return all clinical study materials to the Sponsor, and provide a written statement as to why the premature termination has taken place to the Internal Review Board/Ethics Committee (IRB/EC).

4.0 STUDY ENDPOINTS

4.1 Safety and Performance Measures

- Safety

The assessment of safety will include all occurrences through 30 days post procedure.

Occurrence of Major Adverse Events (MAE) at 30 days

MAE is defined as a composite of all-cause Death, Myocardial Infarction, Stroke, or non-elective Cardiovascular (CV) surgery for device related complications.

- Performance

The assessment of performance measures will include all data reported at 30-day visits for this study.

Clinical Investigation Plan

MR Reduction to $\leq 2+$ at 30 days

4.2 Acute Measures:

- Acute Procedural Success (APS) defined as successful implantation of the MitraClip® device with resulting MR severity of 2+ or less on discharge Echocardiogram (30-day echocardiogram will be used if discharge is unavailable or uninterpretable). Subjects who die or undergo mitral valve surgery before discharge are considered to be an APS failure.
- Acute Device Success defined as successful implant of the MitraClip device without the occurrence of a Device-Related Complication (including mitral valve stenosis, device embolization, Single Leaflet Device Attachment (SLDA), or myocardial perforation) through discharge.
- Procedure Time: defined as the time elapsed from the first intravascular catheter placement or trans-esophageal echocardiogram (TEE) to the removal of the last catheter and TEE.
- Use of Controlled Gripper Actuation (CGA)
- Use of Left Atrial Pressure (LAP) Monitoring
- Number of Attempted Grasps defined as the number of attempts to stabilize leaflets by the open Clip
- Device-Related Complications defined as the occurrence of one of the following adverse events that is determined by investigator assessment to be probably, possibly or definitely related to the MitraClip device.
 - Mitral valve stenosis
 - SLDA
 - Device Embolization
 - Myocardial perforation
 - Need for mitral valve replacement instead of repair due at least in part to the MitraClip procedure or the presence of the MitraClip device
- In-hospital Major Adverse Events (MAE) defined as the number of MAEs that occur prior to discharge from hospitalization in which MitraClip Procedure was performed.

4.3 Clinical Measures

(Discharge, 1, 6 and 12 months, and 2, 3, 4, 5 years):

- All-cause Mortality
- Heart Failure Hospitalization
- MAE as defined above
- Device-Related Complications defined above

MR Reduction to $\leq 1+$ **(Discharge, 1, 12 months, and 5 years)**

- MR Reduction to $\leq 2+$ **(Discharge, 1, 12 months, and 5 years)**

4.4 Functional Improvement Measures

(Baseline, Discharge, 12 months, and 2, 3, 4, 5 years):

- New York Heart Association (NYHA) functional class improvement
- Quality of Life (QOL) assessed using the Kansas City Cardiomyopathy Questionnaire (KCCQ)
- 6 minutes walk distance (6MWD)

Clinical Investigation Plan

4.5 Echocardiographic endpoints:

(Baseline, Discharge, 1, 12 months, and 5 years):

- MR Severity Grade
- Effective Regurgitant Orifice Area (EROA) as measured by PISA method (Baseline only)
- Coaptation Measures (depth/length) (Baseline only)
 - *Coaptation depth: Coaptation depth is defined as the distance from the plane of the mitral valve annulus to the first point of leaflet coaptation in the atrial-to-ventricular direction in the four-chamber view.*
 - *Coaptation length: Coaptation length is defined as the vertical length of leaflets that is in contact, or is available for contact, during systole in the atrial-to-ventricular direction in the four-chamber view.*
- Flail Measures (gap/width) (Baseline only)
 - *Flail Gap: Measured as the greatest distance between the ventricular side of the flail segment to the atrial side of the opposing leaflet. This distance is measured perpendicular to the plane of the annulus in two views and the largest measurement is used. The two views for measurement are the four-chamber long axis (LAX) view and the left ventricular outflow tract (LVOT) view.*
 - *Flail Width: Measured as the width of the leaflet segment that moves in and out of plane during systole in the short axis (SAX) view.*
- Grasping Area Anatomy (measure cleft or scallop if significant) (Baseline only)
- Assess chordal support (Baseline only)
- Regurgitant Jet(s) Position and Quantity (Baseline only)
- TR Severity: None, Mild, Moderate or Severe

5.0 SUBJECT SELECTION AND WITHDRAWAL

5.1 Subject Population

This study will include an analysis of all consented subjects who satisfy the inclusion and exclusion criteria and who are treated with the MitraClip G4 System. The study will include approximately [REDACTED] subjects treated with the MitraClip G4 System that have data available for assessment of APS.

5.2 Subject Screening and Informed Consent

5.2.1 Subject Screening

The hospital will follow their standard of care procedures for determining if a patient is eligible for treatment with a MitraClip System. Consecutive patients who present for their procedure should be asked to provide consent for participation in the MitraClip EXPAND G4 Study if they are eligible per the inclusion/exclusion criteria.

5.2.2 Informed Consent

Patient Information and Consent Form must receive approval of Sponsor and Ethics Committee (EC) or Internal Review Board (IRB) prior to beginning enrollment into the MitraClip EXPAND G4 Study.

Clinical Investigation Plan

The Investigator or designee, who has been trained on the study, will explain the nature and scope, potential risks and benefits of participation, and answer questions for the subjects. The subject will be treated with the MitraClip G4 System per standard of care and must consent only to data collection and follow-up visit schedule. All subjects (or legally authorized subjects' representatives if applicable) must sign, date and time (if required) EC/IRB approved informed consent prior to any data is reported into this study. Obtaining the consent and provisioning of a copy to the subject, must be documented in the subject's medical records. In addition, the signed informed consent must be kept in the subject's medical records.

At sites in the United States, an authorization for use and disclosure of the subject's protected health information, in accordance with the Health Insurance Portability and Accountability Act (HIPAA), must be obtained from the subject or their legally authorized representative. Per site requirements/preference HIPAA elements may be incorporated into the Informed Consent Form (ICF) or it may exist as a standalone document.

If approved by the EC/IRB, subjects from vulnerable populations may be enrolled in the study. The ISO14155 definition of vulnerable population is as follows: individuals who are unable to fully understand all aspects of the investigation that are relevant to the decision to participate, or who could be manipulated or unduly influenced as a result of a compromised position, expectation of benefits or fear of retaliatory response. Examples of populations which may contain vulnerable subjects include: Individuals with lack of or loss of autonomy due to immaturity or through mental disability, persons in nursing homes, children, impoverished persons, subjects in emergency situations, ethnic minority groups, homeless persons, nomads, refugees, and those incapable of giving informed consent. Other vulnerable subjects include, for example, members of a group with a hierarchical structure such as university students, subordinate hospital and laboratory personnel, employees of the sponsor, members of the armed forces, and persons kept in detention.

5.3 Eligibility Criteria

Consecutive consented subjects treated commercially with the MitraClip G4 System should be considered for inclusion in the study. All subjects must meet the criteria below before being enrolled into the MitraClip G4 Study.

5.3.1 Inclusion Criteria

1. Subjects scheduled to receive the MitraClip per the current approved indications for use
2. Subjects who give consent for their participation

5.3.2 Exclusion Criteria

1. Subjects participating in another clinical study that could impact the follow-up or results of this study.

5.4 Subject Enrollment and Inclusion in Analysis

Per ISO 14155, the patient is considered enrolled upon signing and dating an informed consent for participation. Only subjects that have an attempted MitraClip G4 procedure will be included in this analysis.

Clinical Investigation Plan

5.5 Total Expected Duration of the Study

The time to complete the MitraClip EXPAND G4 study is estimated to be approximately █ years.

5.6 Expected Duration of Each Subject's Participation

The final required visit for subjects in the MitraClip EXPAND G4 Study is at █ year post-procedure. Therefore, the expected duration of participation for subjects is approximately █ years.

5.7 Number of Subjects Required to be Included in the Study

Approximately █ subjects will be included in the MitraClip EXPAND G4 Study.

5.8 Estimated Time Needed to Select this Number

The estimated time to include █ subjects in Phase II is about █ years.

5.9 Subject Discontinuation

Subjects that are consented and receive a MitraClip G4 implant shall remain in the study until completion of the required follow-up period; however, a subject's participation in any clinical study is voluntary and the subject has the right to withdraw at any time without penalty or loss of benefit. Conceivable reasons for discontinuation may include, but not be limited to, the following:

- Subject death
- Subject voluntary withdrawal
- Subject lost-to follow-up as described below

The Sponsor must be notified of the reason(s) for subject discontinuation. The site will provide this information to the Sponsor. Investigators must also report this to their respective EC as defined by their institution's procedure(s). No additional follow-up will be required or data recorded from subjects once withdrawn, except for the status (deceased/alive). However, if a subject withdraws due to problems related to the device safety or performance, the investigator shall ask for the subject's permission to follow his/her status/condition outside of the clinical study.

Lost-to-Follow-up:

If the subject misses two consecutive scheduled follow up time points and the attempts at contacting the subject detailed below are unsuccessful, then the subject is considered lost to follow-up. Site personnel shall make all reasonable efforts to locate and communicate with the subject (and document these efforts in the source documents), including the following, at each contact time point:

- A minimum of 2 telephone calls on different days over a 30-day period to contact the subject should be recorded in the source documentation, including date, time and initials of site personnel trying to make contact.
- If these attempts are unsuccessful, a letter (certified if applicable) should be sent to the subject.
- If a subject misses one or more non-consecutive follow-up contact time points it will be considered a missed visit. The subject may then return for subsequent visits. If the subject misses two

Clinical Investigation Plan

consecutive time points and the above-mentioned attempts at communicating with the subject are unsuccessful, the subject will be considered lost-to-follow-up.

Note: Telephone contact with General Practitioner, non-study cardiologist or relative without presence of subject or indirect documentation obtained via discharge letters will not be considered as subject contact.

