5.10 Subject Completion

A Study Completion eCRF must be completed when:

- the subject is considered lost to follow-up per the above definition or
- the subject withdraws from the Study or
- the investigator withdraws the subject from the Study or
- the subject has died or
- upon Study completion (e.g., 5 year follow-up time point has been reached) or
- sponsor termination of Study

Sponsor must be notified of the reason for subject discontinuation. The site will provide this information on the electronic case report form (eCRF). Investigators must also report this to their EC/IRB as defined by their institution's procedure. Subjects will not be replaced.

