5.9 Subject Discontinuation

Subjects that are consented and receive a MitraClip G4 implant shall remain in the study until completion of the required follow-up period; however, a subject's participation in any clinical study is voluntary and the subject has the right to withdraw at any time without penalty or loss of benefit. Conceivable reasons for discontinuation may include, but not be limited to, the following:

- Subject death
- Subject voluntary withdrawal
- Subject lost-to follow-up as described below

The Sponsor must be notified of the reason(s) for subject discontinuation. The site will provide this information to the Sponsor. Investigators must also report this to their respective EC as defined by their institution's procedure(s). No additional follow-up will be required or data recorded from subjects once withdrawn, except for the status (deceased/alive). However, if a subject withdraws due to problems related to the device safety or performance, the investigator shall ask for the subject's permission to follow his/her status/condition outside of the clinical study.

Lost-to-Follow-up:

If the subject misses two consecutive scheduled follow up time points and the attempts at contacting the subject are unsuccessful, then the subject is considered lost to follow-up. Site personnel shall make all reasonable efforts to locate and communicate with the subject.

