#### 2.2.3 Survival Analyses

Survival analysis will be conducted to analyze time-to-event variables, such as all-cause of mortality. Subjects without events will be censored at their last known event-free time point. Survival curves will be constructed using Kaplan-Meier estimates. Summary tables for endpoints will include event (failure)

This confidential document is the property of Abbott and shall not be reproduced, distributed, disclosed or used without the express written consent of Abbott.

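### No vital status is sought for subjects lost to follow-up, although it is kept for withdrawn subjects, so 5-year Kaplan-Meier mortality is understated if loss is related to prognosis

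*Protocol*

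**What the plan says.** **When a subject is lost.** Protocol 5.9 has two conditions, and both must hold: "If the subject misses two consecutive scheduled follow up time points and the attempts at contacting the subject detailed below are unsuccessful". The effort required at each contact time point is stated: "A minimum of 2 telephone calls on different days over a 30-day period to contact the subject should be recorded", followed by a letter if the calls fail.

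**What counts as contact.** A Note reads "Telephone contact with General Practitioner, non-study cardiologist or relative without presence of subject or indirect documentation obtained via discharge letters will not be considered"; its closing words make clear that what such information fails to establish is contact with the subject.

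**What follows.** Protocol 5.10 requires the Study Completion form when "the subject is considered lost to follow-up per the above definition or" any of the other listed end points applies. The sentence in 5.9 that lets a subject come back for later visits is written for non-consecutive misses.

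**Vital status.** The one provision reads "No additional follow-up will be required or data recorded from subjects once withdrawn, except for the status (deceased/alive"). No matching sentence covers lost subjects.

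**Analysis.** SAP 2.2.3 plans Kaplan-Meier estimates: "Subjects without events will be censored at their last known event-free time point". It does not say whether third-party information can set that point. SAP 2.8 uses available data and plans no sensitivity analysis for loss. SAP 3.4 tabulates reasons for early termination.

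**PMCF protocol.** Appendix II 5.9 has the same two-part trigger and says "Site personnel shall make all reasonable efforts to locate and communicate with the subject". It omits the minimum number of calls, the letter and the Note. PMCF subjects are a subset of the main study (Protocol 1.0).

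**The concern.** The plan treats two groups the wrong way round. A subject who has chosen to leave still has deceased/alive status recorded. A subject who never withdrew, but could not be reached, has none sought, even where a treating physician or the family could supply it.

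All-cause mortality is an endpoint through 5 years (Protocol 4.3, SAP 1.4), and the long follow-up is there to confirm safety. Kaplan-Meier estimation assumes that censored subjects have the same later risk as those still followed. If the subjects who stop answering are sicker than the rest, their deaths fall after the censoring date and are not counted. Vital status that is not collected during follow-up may also be hard to recover later.

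**Working it through.** The documents give no expected loss rate and no 5-year mortality figure, so there is no stated number to reproduce. The check has two parts.

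**1. How much time goes unobserved.** Protocol 6.4 sets annual visit windows of -30/+90 days. Take a subject last seen at year 1 who then misses years 2 and 3, with all calls and letters failing.
- Loss is declared at about 3 years + 90 days = 3.25 years.
- Status is already unknown for 3.25 - 1 = 2.25 years by then.
- A further 5 - 3.25 = 1.75 years is never looked at.
- With no other information the subject is censored at year 1, so 4 of the 5 years contribute nothing.

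The earliest pair after discharge is the 30-day visit and the 6-month call. Missing both, with failed contact attempts, leads to closure at about 6 months + 90 days, before the 1-year visit.

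**2. Size of the effect on 5-year mortality.** All inputs are assumptions:
- constant death hazard h = 0.15 per year, which is 1 - exp(-0.15) = 13.9% at 1 year. Appendix VI reports 1-year mortality of 15.3%, 20.3% and 25.8% in three registries;
- a share f of subjects (5%, 10% or 15%) has a potential loss date uniform over 5 years;
- after loss the hazard is multiplied by r (1.5, 2 or 3).

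Kaplan-Meier with censoring at loss estimates 1 - exp(-5h) = 1 - exp(-0.75) = 52.8%, whatever f and r are.

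In the share f, the chance of surviving 5 years is

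S(r) = exp(-0.75r) x [exp(0.75(r-1)) - 1] / [0.75(r-1)]

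- S(1.5) = 0.3247 x 1.2133 = 0.394
- S(2) = 0.2231 x 1.4893 = 0.332
- S(3) = 0.1054 x 2.3211 = 0.245

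For everyone else it is exp(-0.75) = 0.472. The shortfall is f x [0.472 - S(r)], in percentage points:

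| Potential loss f | r = 1 | r = 1.5 | r = 2 | r = 3 |
|---|---|---|---|---|
| 5% | 0 | 0.4 | 0.7 | 1.1 |
| 10% | 0 | 0.8 | 1.4 | 2.3 |
| 15% | 0 | 1.2 | 2.1 | 3.4 |

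At f = 10% and r = 2, true mortality is 52.8 + 1.4 = 54.2%. A simulation of 1,000,000 subjects gives the same 54.2%.

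Some potential-loss subjects die before their loss date. The average chance of being alive at that date is 0.528/0.75 = 0.70, so the share actually lost alive is about 3.5%, 7.0% or 10.6% of the cohort.

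**Sensitivity to the model.** A second model uses an annual loss rate of 2-8% among living subjects and holds the registries' 1-year mortality of 15.3% or 25.8% constant for 5 years. The shortfall is 0.7-2.9 points at r = 1.5, 1.1-5.1 at r = 2, 1.5-8.0 at r = 3, and 0 at r = 1. Direction and zero point agree. The size depends on the assumed loss.

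**The case against.** The strongest reply is that the text is milder than it first appears, and much of that reply stands.

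- **A reader might infer that the Note forbids using a death learned from a relative or a discharge letter.** It does not. It defines contact for deciding who is lost. Protocol 11.2 accepts discharge summaries as support for adverse events, and 7.3.1 requires major adverse events, which include death, to be reported through 5 years. The gap is that nothing asks for status to be sought after closure.
- **A reader might infer that two missed visits close a subject, or that inability to travel does.** Neither is so. The calls and letter must also fail, and speaking to the subject by telephone counts as contact.
- **A reader might infer that Appendix II sets a contrary rule or a different censoring date.** Its trigger is the same with less detail, and neither section 5.9 sets a censoring date. That date comes from SAP 2.2.3.
- **It might be said that the status exception already covers lost subjects**, since it sits under the general discontinuation heading. But 5.9 and 5.10 both list loss and withdrawal as separate reasons, and the exception names only withdrawal.
- **That lost subjects are frailer is an inference.** The documents give no loss rate and no link to prognosis.
- **The stakes are limited.** Phase II tests no hypothesis. With 1,000 Phase II subjects, a 95% interval around 52.8% is about 1.96 x sqrt(0.528 x 0.472/1000) = 3.1 points either way, and only the most extreme cell of the table exceeds that. This is fair, but the interval does not include the bias, and the bias does not shrink as the sample grows.

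**Conclusion.** The point holds as a gap in ascertainment. Followed as written, the plan leaves obtainable deaths unsought in lost subjects and censors those subjects early. Five-year Kaplan-Meier mortality is understated if loss is related to prognosis: by about 0.4 to 3.4 points at a hazard of 0.15 per year, 5-15% potential loss and a post-loss hazard ratio of 1.5-3, and not at all if loss is uninformative. These values are illustrations, not estimates from the documents.

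Acute procedural success, the only tested endpoint, is unaffected, and the 30-day measures little if at all. Heart failure hospitalization could be affected in the same direction, but no size was calculated and none is claimed. The difference from Appendix II is missing detail that should be aligned, not a conflict of rules.

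**What to change.** **Protocol 5.9.** Keep the Note for deciding whether a visit was completed. Extend the deceased/alive exception to lost subjects. Accept documented information from a treating physician, relative, discharge letter or public record for vital status and deaths. Check status at each annual window and at year 5, where consent and local law allow. State that a subject who reappears may resume the schedule.

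**SAP 2.2.3.** State that such information sets the event or censoring date for mortality only. For heart failure hospitalization and other non-fatal events, censor at the last contact at which those events were assessed. Without this limit, a report that the subject is alive would count as time free of hospitalization and bias that endpoint downwards. A sensitivity analysis for subjects whose status stays unknown would be a useful addition, but it does not replace the status check.

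**Appendix II 5.9.** Insert the same text, including the call and letter steps.

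**Cost.** Some site time for a yearly status query on lost subjects, possibly a line in the consent form, and slightly higher reported mortality.
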